- Mean Cumulative Function of PEs reported starting at Day 1 through Week 52 will be created (see Appendix I for technical details)
- Count of PEs within the categories: "0", "1", "2", and ">=3"

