## 8.3. Secondary Endpoints

#### **8.3.1.** Time to First Pulmonary Exacerbation

#### 8.3.1.1. Main Analyses

The Main Estimand of the time to first PE is the On-Study Estimand in which all observed data will be included in the analysis (see Section 2). The ITT Analysis Set (see Section 5.2) will be used for this Estimand. The derivation of the endpoint is detailed in Section 6.7.1.6.

Cumulative first PE incidence rates over the 52-Week treatment period will be calculated using the Kaplan-Meier method. The summary will include the number of participants with at least 1 PE and the number of participants without any events (censored). A covariate-adjusted Cox proportional hazards regression model including fixed effects for treatment group, sputum sample being classified as positive or negative for *Pseudomonas aeruginosa* at Screening Visit, the number of prior PEs [<3 or ≥3] in the previous 12 months, stratification region (North America, Europe, Japan, and the Rest of the World), and age group (adult, adolescent) will be fitted using the PHREG procedure with the robust sandwich estimate for the covariance matrix in SAS (option COVSANDWICH(AGGREGATE) in the procedure-statement). If the age group covariate creates estimability issues, it may be removed. If the model still does not converge after removing the age group covariate, other handling including using the parametric covariance estimator instead of the robust sandwich covariance estimator may be applied. The CLASS statement will identify covariates while the model will be identified in the MODEL statement. Results will be summarized in a table including number and percentage of participants with PEs, estimated hazard ratio and 95%

CONFIDENTIAL Page 57 of 139

confidence limits. The 2-sided Wald p-value from the Cox model will be compared to the appropriate alpha level per the multiple test procedure. Technical details for the implementation in SAS can be found in Appendix I.

Kaplan-Meier estimates of the median including 95% confidence interval will be presented.

The effect over time will be illustrated with a plot of the complement (1 - Kaplan-Meier) estimates).

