### Covariate-adjusted Cox proportional hazards regression model:

#### RUN;

#### Where:

```
trtp participants treatment (1=brensocatib 25mg, 2=brensocatib 10mg, 3=placebo)

region1 stratification factor: region1

psaecol stratification factor: sputum sample being classified as positive or negative for Pseudomonas aeruginosa at screening visit

numpes stratification factor: number of prior Pes [<3 or ≥3] in the previous 12 months

ttpe time to the first PE event (in weeks)

agegr3 adult, adolescent
```

Sorting: data will be sorted by region1, psaecol, numpes, agegr3, ttpe, and usubjid

CONFIDENTIAL Page 117 of 139

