#### **MAIN ANALYSIS**

```
PROC MIXED DATA=<dataIn> EMPIRICAL;
 CLASS usubjid trtpn(REF='3') region1 numpes psaecol atptn;
 MODEL chg=trtpn region1 numpes pasecol baseline
             atptn trtpn* atptn;
 REPEATED atptn / SUBJECT=usubjid TYPE=CS RCORR;
 LSMEANS trtpn*atptn / OM CL DIFF=ALL ALPHA=<>;
 ODS OUTPUT DIFFS=<dataOut>;
RUN;
usubjid
              participants identifier
              participants treatment (brensocatib 10mg, brensocatib 10mg,
trtpn
              placebo)
              stratification factor: North America, Europe, Japan, and
region1
              the Rest of the World
             stratification factor: sputum sample being classified as
psaecol
             positive or negative for Pseudomonas aeruginosa at
              screening visit
```

numpes stratification factor: number of prior PEs [<3 or ≥3] in

the previous 12 months

baseline Baseline post-bronchodilator FEV1

chg Change from baseline for post-bronchodilator FEV1 at

AVISITN (calculated as AVAL-Baseline)

atptn Visit identifier corresponding to the change from baseline

result; refer to the mapping of visits in Section 6.7.5.2

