### **Mean Cumulative Function**

The mean cumulative function will be obtained by PHREG procedure in SAS. Input will be the analysis dataset ADCE. Before calling PHREG, for each participant the time between Pes (event-free time) and the time from last PE until Week 52 needs to be added. This artificial entry will be censored.

An example of the data structure is given below:

Participant	ASTDY	AENDY	CENS	In ADCE	Artificial
1	45	90	0	1	
1	90	122	1		1
1	123	130	0	1	
1	131	319	1		1
1	320	329	0	1	
1	330	364	1		1

```
DATA in1;
  trtpn=1; OUTPUT;
  trtpn=2; OUTPUT;
  trtpn=3; OUTPUT;
RUN;

PROC PHREG DATA=_06cens COVS(AGGREGATE) COVM;
  MODEL (astdy,aendy) * cens(1) = trtpn;
  BASELINE COVARIATES=IN1 OUT=_10phreg CMF=_ALL_ / NOMEAN;
  ID subjid;
RUN;
```

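### The Mean Cumulative Function code treats arm codes 1, 2 and 3 as a number, so the three curves are forced to be proportional and equally spaced on the log scale

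*SAP*

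**What the plan says.** SAP section 8.2.1, among the graphical displays of the primary endpoint, plans this: "Mean Cumulative Function of PEs reported starting at Day 1 through Week 52 will be created (see Appendix I for technical details").

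The code is in Appendix I under Mean Cumulative Function. A covariate data set assigns plain numbers to the treatment variable, beginning with "trtpn=1; OUTPUT" and continuing to 2 and 3. The procedure call "PROC PHREG DATA=_06cens COVS(AGGREGATE) COVM" is followed at once by "MODEL (astdy,aendy) * cens(1) = trtpn". The curves come from "BASELINE COVARIATES=IN1 OUT=_10phreg CMF=_ALL_ / NOMEAN", and an ID statement closes the step. No line declares trtpn categorical or splits the data by arm, and the block does not say which arm each code stands for.

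Elsewhere the SAP handles treatment as categorical:
- The QoL-B code in the same appendix uses the same variable name and has "CLASS usubjid trtpn(REF='3') region1 numpes psaecol atptn".
- The primary GENMOD code, the logistic code for exacerbation-free status, the FEV1 MIXED code and the random-coefficients code all list a treatment variable in CLASS.
- For the Cox model of time to first PE, section 8.3.1.1 says "The CLASS statement will identify covariates while the model will be identified in the MODEL statement".

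Numeric arm codes are printed for the time-to-first-PE model, where the variable is called trtp: "participants treatment (1=brensocatib 25mg, 2=brensocatib 10mg, 3=placebo"). The tipping-point code for that endpoint repeats them for trtn. The QoL-B variable key describes trtpn without numbers and names the 10 mg arm twice.

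**The concern.** PHREG treats a numeric variable that is not in CLASS as continuous. The printed step therefore estimates one coefficient for a one-unit increase in arm code, and the three curves are predictions from that line at 1, 2 and 3. The codes are labels rather than a dose scale, and nothing in either document says that a trend over them is intended.

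The trial compares each of two doses with placebo, and this is the planned cumulative-event figure for the primary endpoint. Readers use such a figure to judge whether the doses differ and when the curves separate from placebo. As coded, spacing and shape are both set by the model. The figure could also visibly disagree with the rate ratios in the primary table, where treatment is categorical.

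**Working it through.** **Inputs.** Protocol section 10.1: placebo rate 1.2 PEs/year, negative binomial dispersion 1, rate ratio 0.70 for either dose (so 0.70 × 1.2 = 0.84), 540 per arm. Protocol section 1.2.2.3 (Phase 2): 10 mg 0.80, 25 mg 0.96, placebo 1.25. The MCF block states no figure to reproduce. As a check that the planning inputs are read correctly: variance of the log rate ratio = (1/1.2 + 1/0.84 + 2)/540 = 0.00745, standard error 0.0863, |log 0.70| = 0.357. Power at two-sided 0.005 is Φ(0.357/0.0863 − 2.807) = 90.7%, against the stated 90%.

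**Model as printed.** λ(t | x) = λ0(t)·exp(βx), with x = 1, 2, 3. The drawn curves are Λ0(t)·exp(β), Λ0(t)·exp(2β) and Λ0(t)·exp(3β). Hence MCF₂(t) = √(MCF₁(t)·MCF₃(t)) at every t, whatever the data.

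**Large-sample fit.** With equal arms, full one-year follow-up and conventional counting-process rows, the fitted Week 52 values f solve Σ(m − f) = 0 and Σx(m − f) = 0, where m is the true one-year mean in each arm and f = exp(a + βx).

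| True values, codes 1 / 2 / 3 | Drawn values | Drawn ratios to placebo | True ratios |
|---|---|---|---|
| Plan: 0.84 / 0.84 / 1.20 | 0.786 / 0.949 / 1.146 | 0.69, 0.83 | 0.70, 0.70 |
| Phase 2, 1 = 25 mg, 2 = 10 mg: 0.96 / 0.80 / 1.25 | 0.862 / 0.996 / 1.152 | 0.75, 0.86 | 0.77, 0.64 |
| Phase 2, 1 = 10 mg, 2 = 25 mg: 0.80 / 0.96 / 1.25 | 0.787 / 0.986 / 1.237 | 0.64, 0.80 | 0.64, 0.77 |

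Check of row 1: 0.786 + 0.949 + 1.146 = 2.881 against 2.88. Weighted by code, 0.786 + 2(0.949) + 3(1.146) = 6.122 against 0.84 + 1.68 + 3.60 = 6.12. And √(0.786 × 1.146) = 0.949.

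In row 1 the code 1 dose is drawn at 0.786/0.949 = 0.83 of the code 2 dose, although the two are equal. In row 2 the order of the doses is reversed. In row 3 the order is right and the distortion is small.

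**Do an arm's own events matter?** Keep the outer arms at 0.84 and 1.20 and move the middle arm's true rate from 0.60 to 1.00. Its drawn value moves from 0.868 to 1.003, and the outer curves move too (code 1 from 0.706 to 0.839, placebo from 1.066 to 1.199). The middle arm's events shift the level of all three curves but cannot set its position between the other two.

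**Simulation.** Gamma-frailty recurrent events, 540 per arm, 15 replicates, so the means carry visible sampling error. At the plan's values, numeric trtpn gives 0.80 / 0.94 / 1.10 and categorical trtpn 0.84 / 0.85 / 1.15. At the Phase 2 rates with code 1 = 25 mg, numeric gives 0.86 / 0.99 / 1.14 and categorical 0.96 / 0.80 / 1.24. The categorical fit keeps the two doses equal in the first case and in the right order in the second; the numeric fit does neither.

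**The case against.** The strongest reply is that this is a slip in one exploratory figure. Section 8.2.1 presents the MCF as a graphical exploration, no contrast or p-value is requested from the model, and none of the twelve hypotheses in section 6.3.1 depends on it. The primary GENMOD code puts treatment in CLASS. Appendix I is not uniformly ready to run: section 8.2.1 calls its primary code an example, and another step is labelled skeleton code. A programmer might correct the line unprompted. All of that stands and limits the weight of the point. It does not make the printed code right: the block is complete from PROC to RUN, and section 8.2.1 refers to it for the technical details.

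Several stronger readings are tempting and not supported:
- A reader might infer that an arm's curve is built only from the other arms' data. It is not; all three arms enter the fit, as the 0.868 to 1.003 shift shows.
- A reader might infer an inflated false-positive rate for one dose. No test is planned from this model.
- A reader might infer that the code reverses the dose order. That needs 1 = 25 mg and 2 = 10 mg together with rates like those in Phase 2. Those codes are printed for trtp and trtn, not for trtpn in this block. With the doses swapped, the Phase 2 rates are distorted little.
- A reader might infer that the trial's reporting loses all view of timing. Section 8.2.1 also plans monthly PE counts with separate bars per arm, and section 8.3.1.1 a plot of one minus Kaplan-Meier for first PE.

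Finally, the drawn values above assume conventional rows. The example rows in the block start at a participant's first PE, and event rows run from PE start to PE end. The numbers therefore illustrate the slope constraint; they do not predict the figure the SAP would produce.

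**Conclusion.** The point holds for this figure. Run as written, the MCF step imposes proportional curves with the middle-coded arm at the geometric mean of the outer two. At the plan's own assumption of two equally effective doses, it draws ratios to placebo of 0.69 and 0.83 where both are 0.70. That size rests on full follow-up, equal arms and conventional counting-process rows. The constraint itself rests only on trtpn being numeric and undeclared, as printed. Which dose is misplaced, and by how much, depends on a coding that the block leaves undefined and on the true rates; there is no distortion of the relative levels only if the log rates happen to be equally spaced in code order. The consequence is a misleading descriptive display of the primary endpoint. The confirmatory analysis, its p-values, the alpha control and the power are untouched. It should be corrected because the error is plain and the correction is nearly free.

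**What to change.** In the Mean Cumulative Function block of Appendix I, state which arm each trtpn code stands for, and estimate the MCF separately in each randomised arm: STRATA trtpn or BY trtpn, with no treatment covariate in MODEL. The covariate data set of codes is then no longer needed. At the least, add CLASS trtpn(REF='3'). That frees the level of each arm but still forces the curves to be proportional, so it would not show when they separate.

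The cost is one or two lines of code and slightly less precise curves than the one-parameter model gives. No new data are needed and no confirmatory test changes.

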# Random coefficients regression model for Rate of Change in Prebronchodilator and Postbronchodilator $FEV_1$ Over the 52-Week Treatment Period

```
PROC MIXED DATA=... METHOD=REML;
CLASS trtp subject;
MODEL FEV1=trtp time trtp*time / S OUTP=prediction DDFM=KR;
RANDOM intercept time / TYPE=UN SUB=SUBJECT;
ESTIMATE "Regr. coeff. Brensocatib 10mg QD" time 1 time*trtp 1 0 0/CL;
ESTIMATE "Regr. coeff. Brensocatib 25mg QD" time 1 time*trtp 0 1 0/CL;
ESTIMATE "Regr. coeff. Placebo QD" time 1 time*trtp 0 0 1/CL;
RUN;
```

CONFIDENTIAL Page 133 of 139

### Estimate of risk difference and exact 95% confidence interval for AESI

```
PROC FREQ DATA=_01get ORDER=DATA;
   TABLE trta * <hypfl,pgfl,infsfl,pneufl> / RISKDIFF(CL=EXACT COLUMN=x);
   EXACT RISKDIFF(METHOD=SCORE);
RUN;
```

Please note that variables  $\langle hypfl, pgfl, infsfl, pneufl \rangle$  are binary (Y/N) with  $\langle hypfl, pgfl, infsfl, pneufl \rangle = Y$  for specific type of AESI, otherwise N.

CONFIDENTIAL Page 134 of 139

### APPENDIX J. TECHNICAL DETAILS FOR PROPOSED MIXTURE-BASED GATEKEEPING PROCEDURE

### Adjusted p values for testing individual null hypotheses

The appendix presents the multiplicity-adjusted p-values for the mixture-based gatekeeping procedure. The following notation will be used:

- The raw p-values are denoted by  $p_1$  through  $p_{12}$ .
- The adjusted p-values are denoted by  $\tilde{p}_1$  through  $\tilde{p}_{12}$ .

The following function will be used to define the multiplicity-adjusted p-values for the individual null hypotheses:

$$f(p,q) = 2\min(p/(1+\gamma_1), q/(1-\gamma_1))$$
, where  $\gamma_1$  is the truncation parameter of Family 1.

The adjusted p-values are given by:

$$\begin{split} \tilde{p}_1 &= \max \left( p_1, \min(2p_{(1)}, p_{(2)}), f(p_1, p_4), f(p_1, p_6), f(p_1, p_8), f(p_1, p_{10}), f(p_1, p_{12}) \right), \\ \tilde{p}_2 &= \max \left( p_2, \min(2p_{(1)}, p_{(2)}), f(p_2, p_3), f(p_2, p_5), f(p_2, p_7), f(p_2, p_9), f(p_2, p_{11}) \right), \\ \tilde{p}_3 &= \max \left( \tilde{p}_1, p_3, f(p_2, p_3), 2 \min(p_3, p_4), 2 \min(p_3, p_6), 2 \min(p_3, p_{10}), 2 \min(p_3, p_{10}), 2 \min(p_3, p_{10}), 2 \min(p_4, p_5), 2 \min(p_4, p_7), 2 \min(p_5, p_6), 2 \min(p_5, p_6), 2 \min(p_5, p_6), 2 \min(p_5, p_6), 2 \min(p_6, p_7), 2 \min(p_6, p_7), 2 \min(p_6, p_7), 2 \min(p_6, p_7), 2 \min(p_7, p_4), 2 \min(p_7, p_6), 2 \min(p_7, p_8), 2 \min(p_7, p_8), 2 \min(p_7, p_8), 2 \min(p_7, p_9), 2 \min(p_9, p_9), 2 \min($$

CONFIDENTIAL Page 135 of 139

### APPENDIX K. DICTIONARY CODES

### WHO DRUG DICTIONARY CODES TO IDENTIFY CHRONIC ANTIBIOTICS USE

Identification of medications will be done using the following criteria:

'ATC2 = 'J01' (ANTIBACTERIALS FOR SYSTEMIC USE) and Route not 'Intravaginal', 'Ophthalmic',' Periodontal', or 'Vaginal''.

# MEDDRA CODES TO IDENTIFY HISTORY OF CHRONIC OBSTRUCTIVE PULMONARY DISEASE (COPD) IN AE AND MEDICAL HISTORY DOMAIN THROUGH COMPARISON OF DATES

### MedDRA codes - PREFERRED TERM

**BRONCHIAL OBSTRUCTION** 

BRONCHITIS: CONDITIONAL ON PARTICIPANTS WITH AN AGE >=18 YEARS ONLY

**BRONCHITIS CHRONIC** 

**CHRONIC BRONCHITIS** 

CHRONIC OBSTRUCTIVE PULMONARY DISEASE

**EMPHYSEMA** 

**OBSTRUCTIVE AIRWAYS DISORDER** 

PULMONARY EMPHYSEMA

### MEDDRA CODES TO IDENTIFY HISTORY OF ASTHMA IN AE AND MEDICAL HISTORY DOMAIN THROUGH COMPARISON OF DATES

### MedDRA codes - PREFERRED TERM

**ASTHMA** 

**ASTHMA LATE ONSET** 

CONFIDENTIAL Page 136 of 139

### WHO DRUG DICTIONARY ATC CODES TO IDENTIFY INHALED STEROID

Get the Inhaled route from CM (cmroute\_std = 110) and then use the ATC4 codes and Preferred Terms as described below:

cmtrt\_atc4\_code in ('R03BA','R03AL')
OR
cmtrt\_atc4\_code = 'R03AK' and
cmtrt\_product contains he following:
'FLUTICASONE' or
'BECLOMETASONE' or
'BUDESONIDE' or
'MOMETASONE' or
'CICLESONIDE' or
'FLUNISOLIDE' or
'BECLOMETHASONE' or
'DEXAMETHASONE' or

'TIXOCORTOL'

### MEDDRA CODES TO IDENTIFY COVID-19 ADVERSE EVENTS

MedDRA codes – PREFERRED TERM	
COVID-19	
SARS-COV-2 TEST POSITIVE	
CORONAVIRUS INFECTION	
COVID-19 PNEUMONIA	

These terms code to SOC = Infections and infestations or Investigations.

CONFIDENTIAL Page 137 of 139

### APPENDIX L. BRONCHIECTASIS SEVERITY INDEX

The calculation of the BSI is included on the eCRF "Bronchiectasis Severity Index", based on the severity criteria reported on the same form. It was decided to re-calculate the BSI by replacing the below severity criteria of the form:

- FEV1 (%Predicted) from pulmonary function test form at Baseline / Day 1, post-bronchodilator; only assessments selected as indicated in Section 6.7.3
- Exacerbation frequency in last 12 months from randomization form
- Colonization status from randomization form

The calculation will be done according to Chalmers et. al (2014) as shown in below table. The source for severity criteria "Age (Years)", "BMI (kg/m²)", "Hospital Admissions in the Past 2 Years", "MRC Dyspnea Score", and "Radiological Severity" will be the eCRF.

Severity Criteria	0 Point	1 Point	2 Point	3 Point	4 Point	5 Point	6 Point
Age (Years)	< 50	-	50 to 69	-	70 to 79	-	80+
BMI (kg/m²)	> 18.5	-	< 18.5	-	-	-	-
FEV 1 (% Predicted)	> 80%	50 to 80%	30 to 49%	< 30%	-	-	-
Hospital Admissions in the Past 2 Years	No	-	-	-	-	Yes	-
Exacerbation Frequency in Last 12 Months	0 to 2	-	3 or More	-	-	-	-
MRC Dyspnea Score	1-3	-	4	5	-	-	-
Colonization Status	Not Colonized	Chronic Colonization	-	Pa Colonization	-	-	-
Radiological Severity	< 3 Lobes Involved	3 or More Lobes or Cystic Changes					

Note: Estimated outcomes are those observed across 5 European treatments in the original derivation and validation study (Chalmers JD et al. 2014). BMI = body mass index, FEV1 = forced expiratory volume in 1 second, MRC = Medical Research Council; Pa = Pseudomonas aeruginosa.

To note: The colonization status will be coded as

- 0 Point for Pseudomonas colonization=No
- 3 Points for Pseudomonas colonization=Yes

This study will have no assignment of "1 Point" for colonization status. Chronic colonization will be considered as "Pa Colonization".

CONFIDENTIAL Page 138 of 139

## APPENDIX M. RULES FOR DIFFERENTIATING CHRONIC ANTIBIOTICS USE

#### Discontinuation from standard of care:

### 1. Identification of therapies:

To identify participants discontinuing from standard of care, the definition of standard of care is important. Participants will be considered being on standard of care is equal to being on a chronic course of antibiotics without any changes in dose nor administration route at baseline. Therapies of interest are those antibiotics who fit into one of the dictionary codes defined in Appendix K. Antibiotic therapies administered to treat a PE are excluded.

2. Combining therapies: this only applies to therapies with multiple records of the exact same CMDECOD name (the coded therapy name):

Any exact same therapies, ignoring a different dose or frequency, will be combined if intake was reported within 7 days, or if records are overlapping.

#### Example 01:

- Antibiotics A: start date=15Jun2022, end date=30Sep2022
- Antibiotics A: start date=02Oct2022, end date=07Mar2023
- In those cases, the start date will be determined as 15Jun2022. The end date will be set to 07Mar2023.

### Example 02:

- Antibiotics B: start date=15Jun2022, end date=30Sep2022
- Antibiotics B: start date=22Sep2022, end date=ongoing
- In those cases, the start date will be determined as 15Jun2022. The end date will be imputed as defined in Section 6.7.1 for PEs ongoing at EOS or the date of data cut-off for data tabulations during study conduct, e.g., dry-runs.

If exact same therapies are more than 7 days apart (>7), the therapies will be considered as two different therapies.

3. Mark therapies who were stable at baseline:

Any antibiotic therapies started prior to the first administration of IP and who were present at day 1 (baseline), including those ongoing at baseline, and who have a minimum duration of 28 days will be considered as standard of care.

4. Identify standard of care marked therapies who stopped during study conduct. Any standard of care therapies present at baseline but stopped during study conduct will be identified through comparison of the therapy stop date against date of last IP administration. Please refer to Section 6.4.2 for determination of date of last IP administration.

CONFIDENTIAL Page 139 of 139

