### PK/PD Substudy

The study will include a PK/PD substudy at select sites with proper laboratory capabilities. The substudy will include approximately 300 adult subjects who are not receiving cyclic antibiotics at Baseline and from whom additional blood PK and sputum PD samples will be collected, with blood PD samples collected from approximately 40 of these subjects. In addition, blood PK and sputum PD samples will be collected from all adolescent subjects who are not receiving cyclic antibiotics at Baseline (blood PD samples will not be collected from adolescents). Adult subjects must provide informed consent to participate in the PK/PD substudy and the blood PD aspect of the PK/PD substudy; the parent or legal guardian must provide informed consent for adolescent subjects.

Sample collections for each aspect of the PK/PD substudy are listed below:

- Blood PK component of the substudy: Blood samples for concentration of study drug will be collected as indicated in Appendix 5.
- Sputum PD component of the substudy: A sputum sample (approximately 3 mL) for NE, CatG, and PR3 concentrations will be collected as indicated in Appendix 6. Sputum induction is allowed for PD sputum sample collection except at Screening (Appendix 1). Adolescent subjects will not be required to produce a sputum sample if they are unable to do so.
- Blood PD component of the substudy (adult subjects in the US only): Blood samples for evaluation of NE, CatG, PR3 and other neutrophil functions will be collected as indicated in Appendix 6.

[figure not shown]
The PK/PD substudy is described in detail in Section 8.

[figure not shown]

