#### 2. STUDY OBJECTIVES AND ESTIMANDS

The treatment effect of brensocatib will be evaluated using the On-Study Estimands primarily; supported using the On-Investigational Product (IP) and On-Treatment Estimands. The treatment regimen in the On-Study Estimand is the randomized assignment to IP irrespective of discontinuation or modifications to standard of care. The On-Study Estimand provides a pragmatic assessment of brensocatib's effectiveness. The treatment regimen for the On-IP estimand is the randomized IP irrespective of modifications to standard of care. The treatment regimen for the On-Treatment Estimand is the randomized IP plus standard of care without addition of new chronic antibiotics during the treatment period or modifications to chronic antibiotics taken at baseline. The On-Treatment estimand describes brensocatib's efficacy.

Note, chronic treatment with antibiotics is permitted for all Estimands if such treatment was initiated at least 3 months prior to Screening. For this study, standard of care is equal to being on a chronic course of antibiotics without any changes in dose nor administration route at baseline. About 20% of participants are on chronic treatment with antibiotics.

The On-Treatment assessment of efficacy is considered supplementary, and will be important in describing the risk:benefit and cost-effectiveness. For this Estimand, the intercurrent event (ICE) of initiation of a new chronic antibiotic during the 52-week treatment period will be defined as any antibiotic intake for more than 28 days other than for the treatment of a concurrent pulmonary exacerbation. Discontinuation from a baseline chronic antibiotic during the 52-week treatment period is also an ICE for the On-Treatment estimand as this can impact the assessment of efficacy. Further, participants randomized but not treated will be excluded from any statistical analysis and data tabulation.

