#### **6.2.1.2.1.** Initiating new Chronic Antibiotic Treatment

Initiation of chronic antibiotics will be identified through entries in eCRF "*Prior and concomitant medications*". World Health Organization (WHO) Drug dictionary codes provided in Appendix K will be used to identify start of new chronic antibiotics. The start date of the new chronic antibiotic must be on or after the date of randomization, and at least 7 days from the end of the previous therapy, if applicable. The date entered for "*Start date*" will be used as date of ICE onset.

Note: it is expected that first IP administration is administered at the date of randomization (refer to Section 6.4.2). In circumstances where the date of first IP is not equal to the date of randomization, the date of first IP administration will be used as reference date. Hence, the start date of the new chronic antibiotic must be on or after the date of first IP administration. This rule applies to the below two sub-sections, too.

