## 6.2.1.2.3. Changing Chronic Antibiotics

Changing existing chronic antibiotics will be identified through entries in eCRF "*Prior and concomitant medications*". WHO Drug dictionary will be used to identify existing and new chronic antibiotics. This ICE subtype applies only in cases where:

- the participant has already (at least) one record for taking chronic antibiotics at time of randomization,
- the start date of the new antibiotic is on or after the date of randomization,
- the existing chronic antibiotic has a stop date entered and the same has not been restarted within 7 days after the stop. Change in dose or frequency of the same chronic antibiotics will be considered as restart,
- the start date of the new antibiotic is within 7 days commencing the stop date of the existing chronic antibiotic.

The date entered for "End date" of the existing chronic antibiotic will be used as date of ICE onset.

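### The 7-day gap rule for chronic antibiotics makes no allowance for planned off-periods, so an unchanged cyclic user can be recorded as stopping standard of care and be cut short in the On-Treatment analysis

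*SAP*

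**What the plan says.** SAP Appendix M derives discontinuation of standard of care in four steps.

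- **Step 2 (joining).** Records with the same coded name, ignoring dose and frequency, "will be combined if intake was reported within 7 days, or if records are overlapping". Beyond that, "If exact same therapies are more than 7 days apart (>7), the therapies will be considered as two different therapies".
- **Step 3 (baseline standard of care).** Antibiotics started before first IP, present at Day 1, and "who have a minimum duration of 28 days will be considered as standard of care".
- **Step 4 (stopping).** "Any standard of care therapies present at baseline but stopped during study conduct will be identified through comparison of the therapy stop date", which is set against the last IP date.

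The main text is consistent with this. SAP 6.2.1.2 does not count a stop if the same drug restarts within 7 days. SAP 6.2.1.2.3 (changing antibiotics) requires that "the existing chronic antibiotic has a stop date entered and the same has not been restarted within 7 days after the stop". SAP 6.2.1.2.1 (initiating a new chronic antibiotic) requires a start on or after randomization and "at least 7 days from the end of the previous therapy, if applicable". SAP 2 sets the threshold for a new chronic antibiotic at more than 28 days of intake, other than for a concurrent exacerbation.

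On who is in the trial, SAP 2 states that "chronic treatment with antibiotics is permitted for all Estimands if such treatment was initiated at least 3 months prior to Screening" and puts chronic users at about 20% of participants. Protocol 5.11.2 has maintenance oral or inhaled antibiotics continue. Cyclic use is a bar only to the substudy (Protocol 3.1): "The substudy will include approximately 300 adult subjects who are not receiving cyclic antibiotics at Baseline". SAP 10.1 plans a PK table restricted to substudy participants not on cyclic antibiotics, so the sponsor expects to be able to identify cyclic users.

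**The concern.** A cyclic regimen contains planned drug-free intervals. A rule that bridges at most 7 days cannot tell such an interval from a real stop. A participant whose treatment has not changed could therefore be given an intercurrent event.

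Four outputs use these events. On-Treatment time at risk ends at the first one (SAP Table 5). The Composite responder estimand imputes non-response when a chronic antibiotic is added (SAP 6.7.2). The jump-to-reference analysis imputes data after the start of an additional chronic antibiotic, and whether it is run at all depends on how many such events there are (SAP 8.2.4). The intercurrent-event tables and time to first event count them directly (SAP 8.4). On-Treatment is supplementary, but SAP 2 says it will inform the benefit-risk and cost-effectiveness description.

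**Working it through.** **Reproducing the plan's examples.** The gap is taken as next start date minus previous end date. In Example 01, 30Sep2022 to 02Oct2022 is 2 days, within 7, so the records join as 15Jun2022 to 07Mar2023, as the SAP states. In Example 02 the records overlap and join. Appendix M does not say how the gap is counted. On this count, an off-period of exactly 7 drug-free days has a difference of 8 and is already split.

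**Assumptions not in the documents.** Cycle length; one medication record per on-period; Day 1 equally likely to fall on any day of the cycle; last IP at Day 364; event onset at the recorded stop date, or at the start date for a new antibiotic.

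**Stop event, 28 on / 28 off.** Let the current on-period have begun k days before Day 1. It runs from Day 1−k to Day 28−k.

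- It is marked standard of care if it began before Day 1 and is still present on Day 1, so k = 1 to 27. Its length of 28 days just meets step 3.
- The next record starts 29 days after it ends, so it is not joined. The stop is dated Day 28−k, from Day 27 down to Day 1, median Day 14.
- Share of Day 1 positions: 27/56 = 48%. In general it is (on−1)/(on+off) when on is at least 28.
- Mean days before the first event: (27×14 + 29×364)/56 = 195.
- The other 29 positions get no event. The drug is not present before and at Day 1, and a later 28-day on-period is not longer than 28 days.

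**Other assumed patterns** (a resumed on-period longer than 28 days is counted as a new chronic antibiotic):

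| On/off days, record format | Positions with a false event | Stop / new | Median day (latest) | Mean days before first event |
|---|---|---|---|---|
| 14/14, separate | 0% | 0 / 0 of 28 | none | 364 |
| 21/7, separate | 0% | 0 / 0 of 28 | none | 364 |
| 28/14, separate | 64% | 27 / 0 of 42 | 14 (27) | 139 |
| 28/28, separate | 48% | 27 / 0 of 56 | 14 (27) | 195 |
| 30/30, separate | 100% | 29 / 31 of 60 | 15.5 (31) | 15.5 |
| 56/28, separate | 100% | 55 / 29 of 84 | 21.5 (55) | 23.5 |
| 28/28, one continuous record | 0% | 0 / 0 of 56 | none | 364 |

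If a resumed baseline drug is not read as new, only the stops remain: 29/60 = 48% for 30/30 and 55/84 = 65% for 56/28.

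**Scale.** Chronic users: 1620 × 0.20 = 324. The cyclic share is not given. At an assumed 10% to 40%, 32 to 130 adults are potentially exposed (2% to 8% of 1620). On 28/28 cycles, 48% of these is about 16 to 62 adults with a false stop. Time lost per cyclic user averages (364−195)/364 = 46%, so the On-Treatment analysis would lose about 0.46 × 2% to 0.46 × 8%, or roughly 1% to 4% of its follow-up, assuming otherwise complete follow-up.

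**Reach.** SAP Tables 1 and 2 handle antibiotic changes by treatment policy in every On-Study main analysis and in the On-IP analyses. On-Treatment applies to the primary endpoint as a supplementary analysis, with an adult repeat (SAP 8.2.6). Table 8 also assigns it to the exploratory CT scores, which have their own SAP.

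**The case against.** The strongest reply is that the error depends on facts nobody can see here. Neither document says how the eCRF holds a cyclic regimen. Step 2 mentions differing frequency, so frequency appears to be captured and one ongoing record is possible; in that case there is no false event. Cycle length and cyclic share are also missing, and on-periods under 28 days give no false event. This stands, and it makes the point conditional.

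Several stronger readings are tempting but not supported:

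- **Every off-period triggers an event.** Only a therapy present at Day 1 is marked standard of care, so at most one stop arises per such therapy.
- **Affected participants leave the analysis.** They are truncated; events and time up to the first intercurrent event still count.
- **A false stop makes a Composite non-responder.** SAP Table 2 handles discontinuation of standard of care by treatment policy there. Only an added chronic antibiotic does this, which needs an on-period over 28 days. Appendix M's steps sit under discontinuation of standard of care, so carrying its two-therapies rule into 6.2.1.2.1 is an inference. That section's wording permits it but does not require it.
- **The treatment comparison is biased.** Treatment is randomized and blinded, so misclassification should be similar across arms. No bias is shown.
- **The time-to-first-PE tipping-point analysis is affected.** A note in Appendix I says participants with intercurrent events are censored. SAP 8.3.1.2, however, describes imputation after study withdrawal under the On-Study estimand, so this is not counted.

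The blinded data review (SAP 6.2) is a partial safeguard: it agrees actions for participants meeting event criteria before lock. It has no written criterion for planned off-periods, so it does not by itself correct the rule.

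**Conclusion.** The rule has a real gap. As written, it can record an unchanged cyclic regimen as a discontinuation of standard of care and end On-Treatment time at risk within about four weeks of Day 1 for 28-day on-periods, or eight weeks for 56-day on-periods. This requires separate records per on-period, on-periods of at least 28 days and off-periods over 7 days. With on-periods over 28 days, a resumed on-period can also be read as a new chronic antibiotic, which would carry the error into the Composite and jump-to-reference analyses.

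The rule also has a reverse weakness. A cyclic user in an off-period at Day 1, or with separately recorded on-periods under 28 days, is never marked as on standard of care, so a genuine later stop would be missed.

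The size is unknown; the 32 to 130 exposed adults rest on an assumed cyclic share. The effect is confined to the On-Treatment and Composite analyses, the conditional jump-to-reference analysis and the intercurrent-event summaries. No On-Study primary or secondary main result changes. It is worth correcting before lock because the correction is cheap.

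**What to change.** Before intercurrent events are derived:

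1. State how cyclic regimens are recorded, and flag cyclic baseline regimens at the blinded data review.
2. In Appendix M step 2 and SAP 6.2.1.2, join on-periods of the same baseline antibiotic (same CMDECOD) across the planned off-period plus 7 days, and say how the gap is counted. For 28/28 cycles, a limit of 28 on start minus end still fails because the difference is 29.
3. Treat a flagged participant in a planned off-period at Day 1 as on standard of care.
4. Count discontinuation only when the next due on-period is not started.
5. Do not count an on-schedule restart as a new chronic antibiotic. Keep the existing rule for a restart after a gap longer than the planned off-period plus 7 days; exempting every restart would hide a real stop and later resumption.
6. Reconcile the 28-day minimum in Appendix M step 3 with the more-than-28-day threshold in SAP 2. The two diverge exactly at a 28-day on-period.

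Bridging alone (item 2) raises mean days before the first event from 195 to 357 of 364 for 28/28 (limit 29 days), and from 15.5 to 356 for 30/30 (limit 35 days). The remaining events fall in the last weeks, where the final off-period straddles last IP; item 4 removes them.

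The cost is SAP wording, a change to the derivation program, and a blinded manual review of cyclic users' medication records. Where the off-period is not captured directly, it has to be taken from those records.
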